5.3.2.2. Exclusion of implausible solicited Event

Some local and systemic events will be directly measured by the subject and will be subject to a reconciliation process, even if they are biologically implausible. Therefore, these implausible measurements will be removed from the analysis but included in listings. Implausible measurements are summarized in the table below:

CONFIDENTIAL209544 (RSV MAT-004)
Statistical Analysis Plan Amendment 3**Table 8 Implausible Solicited Events**

Parameter	Implausible measurements
Body temperature	≤ 33°C or ≥ 42°C
Erythema	Measurements < 0 mm For subjects ≥ 6 years: ≥ 900 mm
Swelling	Measurements < 0 mm For subjects ≥ 6 years: ≥ 500 mm

5.3.2.3. Analysis of Unsolicited Adverse Events

The analysis of unsolicited events will be performed on Exposed Set

5.3.2.4. Combined Solicited and Unsolicited Adverse Events

The combined analysis of solicited and unsolicited events will be performed on Exposed Set. A summary of subjects with all combined solicited and unsolicited adverse events will be provided.

Solicited adverse events will be coded by MedDRA as per the following codes

Solicited symptom	Lower level term code	Corresponding Lower level term decode
Pain	Injection site pain	10022086
Redness	Redness at injection site	10022098
Swelling	Swelling at injection site	10053425
Fatigue	Fatigue	10016256
Fever	Fever	10016558
Nausea	Nausea	10028813
Vomiting	Vomiting	10047700
Diarrhea	Diarrhea	10012727
Abdominal pain	Abdominal pain	10000081
Headache	Headache	10019211

Please note – to check for AE term in cDISC during dry run

For clintrial.gov and EudraCT posting purposes, a summary of combined solicited and unsolicited adverse events will be produced by System Organ Class and preferred terms and according to occurrence of each event.

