4.1.1. Maternal Subjects

	Description
Analysis Set	Maternal subjects
Enrolled	All maternal subjects who completed the informed consent process and signed the informed consent form.
Exposed	All maternal subjects who received at least 1 dose of the study intervention. The allocation in a group is done in function of the administered intervention.
Full Analysis	All maternal subjects in the Exposed set who have post-vaccination immunogenicity data.
Per Protocol	All maternal subjects who received at least 1 dose of the study intervention to which they were randomised and have post-vaccination data (Full Analysis Set) minus subjects with protocol deviations that lead to exclusion.
Unsolicited Safety	All maternal subjects who received at least 1 dose of the study intervention (Exposed Set) that report unsolicited AEs/report not having unsolicited AEs
Solicited Safety	All maternal subjects in the Exposed Set who have solicited safety data

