4.2.4.1.2. Solicited safety set

Code 1030 (Study vaccine not administered at all), code 800 (fraudulent data) and code 900 (invalid informed consent) and code 1160 (no post-vaccination solicited safety data) will be used for identifying subjects eliminated from the solicited safety set.

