Safety analyses in **infant subjects** will include summaries by study group and gestational age at birth (> 37 weeks or ≤ 37 weeks) of neonatal AESIs, MAEs, SAEs, AEs leading to study withdrawal, and the occurrence of RSV-associated RTIs, LRTIs, severe LRTIs, very severe LRTIs and RSV-associated hospitalizations.

All safety analyses will be performed on the Solicited Safety or Exposed sets.

	Primary Safety Endpoints	Statistical Analysis Methods
Maternal subjects	Occurrence of Solicited administration site and systemic events that occur during a 7-day follow-up period after vaccination (i.e. the day of vaccination and 6 subsequent days).	
The number and percentage with exact 95% CI of maternal subjects reporting each Solicited administration site event (any grade, each grade,) and solicited systemic event (any, each grade) during the 7-day (days 1 to 7) follow-up period after vaccination will be tabulated by maximum intensity per subject for each study vaccine group.
 
For fever during the 7-day follow-up period after vaccination, the number and percentage of maternal subjects reporting any fever (i.e., temperature ≥ 38 °C) and fever by half degree (°C) cumulative increments, any Grade 3 fevers, will be reported. In addition, the prevalence of any and Grade 3 fever will be presented graphically over time after vaccination.
 
The number and percentage of maternal subjects with at least one administration site AE (solicited and unsolicited), with at least one systemic AE (solicited and unsolicited) and with any AE during the 7-day follow-up period after vaccination will be tabulated with exact 95% confidence interval (CI) by group. The same computations will be done for Grade 3 solicited and unsolicited AEs, for any AEs considered related to vaccination, for any Grade 3 AEs considered related to vaccination and for any AEs resulting in a medically attended visit (i.e., MAEs).

	Occurrence of any protocol-specified hematological or biochemical laboratory abnormality at baseline (up to 15 days before vaccination) and Day 8 (Visit 2)	The number and percentage of subjects with hematology and biochemistry results outside central laboratory normal ranges will be tabulated to show Day 8 versus baseline. The maximum grading as described in [Sheffield, 2013] and in the SPM from Screening up to Day 8 will also be tabulated.

CONFIDENTIAL209544 (RSV MAT-004)
Statistical Analysis Plan Amendment 3

	Primary Safety Endpoints	Statistical Analysis Methods

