Infant subjects	
From birth through 6 months (Visit 4-NB) after birth, occurrences of SAEs, AEs leading to study withdrawal, and medically attended AEs
 
From birth through 1 year (Visit 5-NB) after birth, occurrences of SAEs, AEs leading to study withdrawal, and MAEs
	
For each category:
 
 - SAE, - MAEs 
The number and proportion of infant subjects who experienced at least one event from birth up to 6 months after birth and the number and proportion of infant subjects who experienced at least one event from birth up to 1 year after birth will be tabulated with 95% CI by group.
 
By-subject listings of SAEs, AEs leading to study withdrawal and MAEs will be prepared.

	
From birth to 6 months after birth (Visit 4-NB), occurrences of RSV-associated LRTI(s), Severe LRTI(s), very severe LRTIs and RSV-associated hospitalizations (according to the case definitions in Section 4.2.6 in the protocol)
	
For each category:
 
 - RSV-associated LRTI, - Severe LRTI, - Very severe LRTI - RSV-associated hospitalization 
The number and proportion (with 95% CI) of subjects with at least one event will be calculated and tabulated by group.

CONFIDENTIAL209544 (RSV MAT-004)
Statistical Analysis Plan Amendment 3**5.3.2. Additional considerations****5.3.2.1. Analysis of solicited events**

The analysis of solicited events will be performed on Solicited Safety Set. The intensity of the following solicited events will be assessed as described:

Table 7 Intensity scales for solicited symptoms in adults

Adults/Child (≥6 years)		
Adverse Event	Intensity grade	Parameter
Pain at injection site	0	None
	1	Mild: Any pain neither interfering with nor preventing normal every day activities.
	2	Moderate: Painful when limb is moved and interferes with every day activities.
	3	Severe: Significant pain at rest. Prevents normal every day activities.
Redness at injection site		Record greatest surface diameter in mm
Swelling at injection site		Record greatest surface diameter in mm
Temperature		Record temperature in °C/°F (with 1 decimal) Temperature will be analysed in 0.5°C increments from ≥ 38.0°C /100.4°F) Grade 3 fever is defined as > 39.0°C /102.2°F
Headache		
Fatigue	0	Normal
Nausea	1	Mild: Easily tolerated
Vomiting	2	Moderate: Interferes with normal activity
Diarrhea	3	Severe: Prevents normal activity
Abdominal pain		

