10.1.2.3. Daily recording of solicited events**10.1.2.3.1. Studies with electronic diaries**

For studies using electronic diaries for the collection of solicited adverse events, a solicited adverse event will be considered present only when a daily recording of grade 1 or more is present.

CONFIDENTIAL209544 (RSV MAT-004)
Statistical Analysis Plan Amendment 3**10.1.2.4. Unsolicited adverse events**

Unsolicited adverse event summaries are including serious adverse events unless specified otherwise.

Missing severity, relationship with study vaccine, and outcome of unsolicited adverse events will not be replaced and will appear as 'UNKNOWN' in all statistical output.

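### The combined solicited-plus-unsolicited AE tables divide by all dosed women, including those with no solicited data, so their percentages are diluted and not comparable with the single solicited-event rates

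*SAP*

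**What the plan says.** All references are to the current SAP (Amendment 3).

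- **Solicited events (5.3.2.1):** "The analysis of solicited events will be performed on Solicited Safety Set". Section 4.1.1 defines that set as maternal subjects in the "Exposed Set who have solicited safety data". Section 4.2.4.1.2 removes women with none by code 1160, which is not among the Exposed Set elimination codes in 4.2.1.
- **Unsolicited events (5.3.2.3):** "The analysis of unsolicited events will be performed on Exposed Set".
- **Combined tables (5.3.2.4):** "The combined analysis of solicited and unsolicited events will be performed on Exposed Set". For mothers that set is "All maternal subjects who received at least 1 dose of the study intervention" (4.1.1), with no requirement that safety data were returned.
- **Outputs concerned (5.3.1, primary safety rows):** women with at least one administration-site AE, at least one systemic AE, and "with any AE during the 7-day follow-up period after vaccination will be tabulated with exact 95% confidence interval (CI) by group". The same is planned over 30 days, with repeats for Grade 3, related and medically attended events.
- **Diary rule (10.1.2.3.1):** "a solicited adverse event will be considered present only when a daily recording of grade 1 or more is present".

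Section 5.3.1 says in general terms that safety analyses use either the Solicited Safety or the Exposed set. The SAP does not reconcile the two denominators, and it plans no supportive combined table on a common set.

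**The concern.** The same solicited events are counted over two denominators. A woman with no solicited data is excluded from the injection-site pain table because her status is unknown. In the combined table she is kept, and the diary rule makes her unknown status count as no solicited event. For solicited events the error can only go downward.

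Two readings of the tables suffer. First, a combined percentage can fall below one of its own components in the same report, which cannot happen on a single denominator. Second, if groups differ in how many women have no solicited data, the combined rates are diluted unequally. The safety tables are descriptive and carry no test, so the displayed percentage is itself the result.

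**Working it through.** The SAP states no figure on this point, so there is none to reproduce. The check is direct arithmetic.

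**Inputs**

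- N_E, exposed women in a group. The change table in the Amendment 2 document history reports 213 vaccinated. With exactly equal allocation, 213/3 = 71. This serves only to size the illustration.
- m, exposed women with no solicited data. Not given; 0 to 10 shown.
- N_S = N_E − m, the Solicited Safety Set.
- x, women with the solicited component (for example pain). Its rate is not given; about 50% and 60% shown.
- a, women who have the combined outcome but not that component.

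**Size of the dilution.** Let c be the women with solicited data who have the combined outcome, and u the women without solicited data who enter through an unsolicited AE. The Solicited Safety Set gives c/N_S; the Exposed Set gives (c + u)/N_E. With u = 0 the ratio of the second to the first is N_S/N_E = 1 − m/N_E. For m = 3 that is 68/71 = 0.958. With u above 0 the dilution is smaller, and it vanishes when women without a diary report events at the same rate as the others.

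**When a combined rate falls below its component.** The solicited table shows x/N_S and the combined table (x + a)/N_E. Inversion occurs exactly when a < x·m/N_S.

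Example with N_E = 71, m = 3, x = 40: the threshold is 40 × 3/68 = 1.76, so a = 1 inverts. Clopper-Pearson intervals are in brackets, and the one added woman is assumed to have solicited data.

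- Component: 40/68 = 58.8% (46.2 to 70.6)
- Combined, Exposed Set: 41/71 = 57.7% (45.4 to 69.4), below the component
- Combined, Solicited Safety Set: 41/68 = 60.3% (47.7 to 72.0), above it

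**Range, N_E = 71**

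| m | Component x/N_S | Combined, Exposed Set | Inverted for |
|---|---|---|---|
| 0 | 43/71 = 60.6% | 43/71 = 60.6% (a = 0) | never |
| 1 | 42/70 = 60.0% | 42/71 = 59.2% (a = 0) | a = 0 |
| 3 | 34/68 = 50.0% | 35/71 = 49.3% (a = 1) | a up to 1 |
| 5 | 40/66 = 60.6% | 42/71 = 59.2% (a = 2) | a up to 3 |
| 10 | 37/61 = 60.7% | 39/71 = 54.9% (a = 2) | a up to 6 |

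With a = 0 and a component near 60%, the loss is 0.8 percentage points at m = 1, 4.3 at m = 5 and 8.6 at m = 10.

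**Where inversion is plausible.** It needs a small a. The administration-site row is the natural candidate: the solicited site events are only pain, redness and swelling, redness and swelling score above 0 only beyond 20 mm (5.3.2.1), and SAEs are always counted as general events (10.1.3.10).

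**The case against.** Keeping every dosed woman in a table that includes unsolicited AEs and SAEs is a defensible safety convention, and 5.3.1 names both sets. Moving the combined tables wholly to the Solicited Safety Set would drop observed events. If the only Grade 3 AE in a group occurred in one of 7 women without a diary, the unsolicited table would show 1/71 (1.4%) and the combined table 0/64. This stands, and it is why the Exposed Set should not simply be replaced. The single solicited-event rates already use the right set, and no decision rule depends on the combined percentages. That also stands.

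Four stronger readings are tempting, but the document does not support them.

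- **That women who withdrew or stopped the diary count as event-free.** Code 1160 covers only women with no solicited data. A woman with some entries is in both sets and her recorded events count in both.
- **That the rate is always multiplied by one minus the fraction without a diary.** That is the worst case. Going from 48/64 = 75.0% to 48/71 = 67.6% assumes that none of the 7 women reported any unsolicited AE, which is least credible over 30 days.
- **That any AE will fall below pain.** In that example pain would need at least 44/64 = 68.8%, leaving at most 4 of the 48 women whose AE was something other than pain, across all other solicited symptoms and every unsolicited AE. This is remote.
- **That a false group difference follows.** It requires unequal loss of diaries. An assumed 2% against 15% turns a common 75% into 73.5% and 63.8% at worst, but the SAP gives no figure for loss in any group, and subjects stay blinded throughout.

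**Conclusion.** The mismatch is explicit and nothing in the SAP corrects it. In any group that contains women with no solicited data, the maternal combined percentages are diluted by at most the fraction without such data, relative to the Solicited Safety Set figure. They can then fall below a component, most plausibly for at least one administration-site AE against injection-site pain: 57.7% against 58.8% in the example.

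The mechanism rests on the text alone. The size rests on assumptions: 71 women per group, the number without a diary, the component rate and how many women other events add. With complete diaries there is no effect, and with one or two missing it is slight. No error rate or test is involved. This is a denominator weakness in primary safety tables that is cheap to repair, not a flaw that invalidates them.

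**What to change.** In 5.3.2.4, and in the 7-day and 30-day combined rows of 5.3.1:

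1. Keep the maternal combined tables on the Exposed Set, so that no observed unsolicited AE or SAE is lost, and use that version for registry posting.
2. Show beside them, by group, the number of exposed women with and without solicited data.
3. Add the same 7-day and 30-day tables on the Solicited Safety Set, and state that this version is the one to use when combined rates are compared with single solicited-event rates or between groups.

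On the Solicited Safety Set the combined figure is (x + a)/N_S, with a counted within that set, so it cannot fall below x/N_S. The cost is a few lines of SAP text and one additional set of tables from existing programs.

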5.3.2.5. Analysis of RTI and LRTI

The analysis of RTI and LRTI will be performed on Exposed Set according to the case definitions in section 9.1.3. Separate listings of maternal MA-RTI and infant RTI/LRTI will be provided.

Further analysis with respect to the incidence of RSV LRTI by an exploratory case definition might be performed if deemed necessary.

CONFIDENTIAL209544 (RSV MAT-004)
Statistical Analysis Plan Amendment 3**5.3.2.6. Other analysis**

Other safety analysis will be performed on Exposed Set.

For hematology and biochemistry lab results, the maximum grading as described in [Sheffield, 2013] and SPM will be used, see section 9.1.4 for details.

Concomitant medications will be coded using the GSKDRUG dictionary. The number and percentage of maternal subjects taking concomitant medications (any medication, any antipyretic and any antipyretic taken prophylactically, respectively) within 7 days following vaccination, 30 days following vaccination, up to 6 weeks post-delivery and up to 6 months post-delivery will be summarized by group. A listing will also be provided.

The number and percentage of infants taking concomitant medications from birth up to 6 weeks after birth, 6 months after birth and 1 year after birth will be summarized by group. A listing will also be provided.

6. ANALYSIS INTERPRETATION

All comparative analyses will be descriptive with the aim to characterise the difference in immunogenicity between groups. These descriptive analyses should be interpreted with caution considering that there is no adjustment for multiplicity for most of these comparisons.

7. CONDUCT OF ANALYSES**7.1. Sequence of analyses****7.1.1. First analysis**

The **first analysis** will be conducted after approximately 75 maternal subjects have completed Visit 3 (Day 31) and approximately 24 maternal subjects and their infants have completed Visit 5 / Visit 1-NB (Delivery/Birth).

By-study-group safety and immunogenicity analyses will be performed by an independent statistician not affiliated with the project (to preserve the observer blinding).

Immunogenicity analyses will include all available test results at:

- Visit 1 (Day 1) and Visit 3 (Day 31);
- Visit 5 (delivery; maternal blood sample and cord blood). If no cord blood was collected, test results for the infant blood sample collected within 3 days post birth (Visit 1-NB) will also be evaluated.

Safety analyses will be performed by blinded treatment group, with the letters “A,” “B,” and “C” replacing treatment-specific group identifiers in all results summaries. Steps will be taken to minimize the risk of unblinding (e.g., events that happen in a single group will be masked by adding the same amount of counts to other groups). Although the risk of unblinding may be reduced with the proposed masking, this risk may not be avoidable in certain cases.

CONFIDENTIAL209544 (RSV MAT-004)
Statistical Analysis Plan Amendment 3

Safety analyses will include all available data for:

- Solicited events, unsolicited AEs for 30 days post-dose, MAEs, SAEs and AESIs.
- RTI surveillance data (including nasal swab test results).

A report summarizing these **safety and immunogenicity** results will be prepared but will not be made available to investigators.

No individual (by-subject) data / data listings will be provided, except for SUSARs which will be reported to regulatory authorities in compliance with the regulations.

7.1.2. Second analysis (**Amended 02-NOV-2020**)

The **second analysis** will be performed after approximately 24 maternal subjects and their infants have completed Visit 7 / Visit 3-NB (Day 121 post-delivery / birth).

By-study-group immunogenicity and by-study-group safety analyses will be performed by an independent statistician not affiliated with the project (to preserve the observer blinding).

By-study-group immunogenicity analyses will include all available test results, at:

- Visit 1 (Day 1) and Visit 3 (Day 31).
- Visit 5 (delivery; maternal blood sample and cord blood). If no cord blood was collected, test results for the infant blood sample collected within 3 days post birth (Visit 1-NB) will also be evaluated.
- Visit 6 / Visit 2-NB (Day 43 post delivery).
- Visit 3-NB (Day 121 post-delivery).

By-study-group safety analyses will include the following data from those subjects who have reached the Day 43 post-delivery visit:

- Solicited events, unsolicited AEs for 30 days post-dose, MAEs, SAEs and AESIs.
- RTI surveillance data (including nasal swab test results).

Safety results that would lead to the unblinding of some subjects (e.g. a specific AE reported by one subject only) will be masked (i.e. the group in which this event occurred will not be identified). ***Although the risk of unblinding may be reduced with the proposed masking, this risk may not be avoidable in certain cases.***

Blinded SAE and AESI listings for all subjects will also be provided.

The results will be summarized in an Investigator Brochure update.

No individual (by-subject) data / data listings will be provided, except for SUSARs which will be reported to regulatory authorities in compliance with the regulations.

CONFIDENTIAL209544 (RSV MAT-004)
Statistical Analysis Plan Amendment 3**7.1.3. Third analysis (Amended 02-NOV-2020)**

The **third analysis** will be performed after approximately 150 maternal and infant subjects have completed Visit 8/Visit 4-NB (Day 181 post-delivery/birth).

By-study-group immunogenicity and by-study-group safety analyses will be performed by an independent statistician not affiliated with the project (to preserve the observer blinding).

By-study-group immunogenicity analyses will include all available test results at:

- Visit 1 (Day 1) and Visit 3 (Day 31);
- Visit 5 (delivery; maternal blood sample and cord blood). If no cord blood was collected, test results for the infant blood sample collected within 3 days post birth (Visit 1-NB) will also be evaluated.
- Visit 6 / Visit 2-NB (Day 43 post delivery);
- Visit 3-NB (Day 121 post-delivery)
- Visit 4-NB (Day 181 post-delivery)

By-study-group safety analyses will include the following data from all **vaccinated** subjects who have reached the Day 43 post-delivery visit:

- Solicited events, unsolicited AEs for 30 days post-dose, MAEs, SAEs and AESIs.
- RTI surveillance data (including nasal swab test results).

Safety results that would lead to the unblinding of some subjects (e.g. a specific AE reported by one subject only) will be masked (i.e. the group in which this event occurred will not be identified). ***Although the risk of unblinding may be reduced with the proposed masking, this risk may not be avoidable in certain cases.***

In addition, blinded SAE and AESI listings for all subjects will be provided.

The results will be summarized in an Investigator Brochure update.

No individual (by-subject) data / data listings will be provided, except for SUSARs which will be reported to regulatory authorities in compliance with the regulations.

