To evaluate pregnancy outcomes and pregnancy-related AESIs after a single IM dose of study vaccine administered to maternal subjects, from Visit 1 up to 6 weeks after delivery (Visit 6).	Pregnancy outcomes from Day 1 (Visit 1) up to 6 weeks after delivery (Day 43 post-delivery, Visit 6). These include live birth with no congenital anomalies, live birth with congenital anomalies, fetal death/still birth (antepartum or intrapartum) with no congenital anomalies, fetal death/still birth (antepartum or intrapartum) with congenital anomalies, elective/therapeutic termination with no congenital anomalies and elective/therapeutic termination with congenital anomalies.
	Pregnancy-related AESIs from Day 1 (Visit 1) up to 6 weeks after delivery (Day 43 post-delivery, Visit 6). These include but are not limited to maternal death, hypertensive disorders of pregnancy (gestational hypertension, pre-eclampsia, pre-eclampsia with severe features including eclampsia), antenatal bleeding (morbidly adherent placenta, placental abruption, cesarean scar pregnancy, uterine rupture), postpartum hemorrhage, fetal growth restriction, gestational diabetes mellitus, non-reassuring fetal status, pathways to preterm birth (premature preterm rupture of membranes, preterm labor, provider-initiated preterm birth), chorioamnionitis, oligohydramnios, polyhydramnios, gestational liver disease (intrahepatic cholestasis of pregnancy, acute fatty liver of pregnancy), maternal sepsis.*
To evaluate the safety of the study vaccine, including neonatal AEs of special interest, in infants born to maternal subjects who were vaccinated with a single IM dose of study vaccine, up to 6 weeks after birth.	The occurrence of neonatal AEs of special interest (reported up to 6 weeks after birth). These include but are not limited to small for gestational age, low birth weight including very low birth weight, neonatal encephalopathy, congenital microcephaly (postnatally or prenatally diagnosed), congenital anomalies (major external structural defects, internal structural defects, functional defects), neonatal death (in a preterm live birth or in a term live birth), neonatal infections (blood stream infections, meningitis, respiratory infection), respiratory distress in the neonate, preterm birth, failure to thrive, large for gestational age, macrosomia.* Occurrence of SAEs, AEs leading to study withdrawal and MAEs from birth up to 6 weeks after birth.

CONFIDENTIAL209544 (RSV MAT-004)

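### Read literally, the second and third by-group safety tables drop mothers and infants who died or withdrew before the Day 43 post-delivery visit; the SAP should say that they stay in

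*SAP*

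**What the plan says.** Section 7.1.2 (second analysis) restricts the by-group safety data: "By-study-group safety analyses will include the following data from those subjects who have reached the Day 43 post-delivery visit". The data concerned are solicited events, unsolicited AEs, MAEs, SAEs, AESIs and respiratory surveillance. Section 7.1.3 (third analysis) covers vaccinated subjects under the same condition, "subjects who have reached the Day 43 post-delivery visit". Of the results, 7.1.2 says: "The results will be summarized in an Investigator Brochure update". Section 7.1.3 says the same.

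Other parts of the SAP describe the safety population without a visit condition:

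- Section 7.1.1 (first analysis): "Safety analyses will include all available data for" the listed event types.
- Section 5.3.1: "All safety analyses will be performed on the Solicited Safety or Exposed sets".
- Section 4.1.1, maternal Exposed Set: "All maternal subjects who received at least 1 dose of the study intervention".

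Table 1 makes maternal death (a pregnancy-related AESI, to Day 43 post-delivery), neonatal death (a neonatal AESI, to 6 weeks after birth) and AEs leading to study withdrawal part of the primary safety endpoints over this window.

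For all subjects regardless of visit, 7.1.2 promises: "Blinded SAE and AESI listings for all subjects will also be provided". Section 7.1.3 makes the same promise.

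**The concern.** The condition for entering the table is a milestone after vaccination, and some of the outcomes to be counted prevent a subject from reaching it. An infant who dies in the first weeks, a mother who dies, or a subject withdrawn because of an AE has no Day 43 visit. If the flag is programmed from visit records, the event and its subject both disappear, and the group's rates are then computed among those who survived and stayed.

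Leaving out subjects whose Day 43 is not yet due is ordinary administrative censoring and does no harm. The difficulty is that the same words also remove deaths and withdrawals, and nothing in either section adds them back. What is at stake is the by-group picture of SAEs and AESIs given to investigators through the Investigator Brochure for a vaccine given in pregnancy.

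**Working it through.** The SAP states no figure for this restriction, so there is none to reproduce. The check compares the texts and then illustrates the size.

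**Texts side by side**

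| SAP section | Safety population | Visit condition |
|---|---|---|
| 5.3.1 | Solicited Safety or Exposed sets | none |
| 5.3.2.3 to 5.3.2.6 (unsolicited, combined, RTI/LRTI, other safety) | Exposed Set | none |
| 4.2.1 | leaves the Exposed Set only by codes 1030, 800, 900, 901 | none |
| 7.1.1 | all available data | none |
| 7.1.2, 7.1.3 | reached the Day 43 post-delivery visit | yes |
| 7.1.4 | all primary and secondary endpoint data | none |

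No elimination code refers to death, withdrawal or a missed Day 43 visit. The condition appears only in 7.1.2 and 7.1.3.

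**Inputs**

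- 213 vaccinated (document history of SAP Amendment 2), allocated 1:1:1 (section 3): 213/3 = 71 per group.
- Clopper-Pearson 95% intervals, as in section 10.1.5.1. For 0 of n the upper limit is 1 − 0.025^(1/n).
- Assumed: k deaths before Day 43, all in one group, no other losses.

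**Display under the literal rule and on the Exposed Set**

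| k | Literal rule | Exposed Set |
|---|---|---|
| 1 | 0/70 (0-5.1%) | 1/71 = 1.4% (0.04-7.6%) |
| 2 | 0/69 (0-5.2%) | 2/71 = 2.8% (0.3-9.8%) |
| 3 | 0/68 (0-5.3%) | 3/71 = 4.2% (0.9-11.9%) |

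**How often a group would lose someone.** With p the assumed risk of death or withdrawal before Day 43, P(at least one) = 1 − (1 − p)^71.

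| p | Expected loss, 71p | P(at least one) |
|---|---|---|
| 1% | 0.7 | 51% |
| 2% | 1.4 | 76% |
| 5% | 3.6 | 97% |
| 10% | 7.1 | over 99% |

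**Effect on an SAE rate.** Assume a 10% SAE risk in those who reach the visit and 5% leaving early:

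- SAE risk 50% in early leavers: 0.05 × 0.50 + 0.95 × 0.10 = 12.0%
- SAE risk 100% in early leavers: 0.05 × 1.00 + 0.95 × 0.10 = 14.5%

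The table would show 10% in both cases.

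**Where 71 applies.** It fits the third analysis at best. The second is triggered when about 24 mother-infant pairs have completed Day 121, and the number past Day 43 at that time is not stated. Section 4.1.2 admits only live-born infants with consent to the infant Exposed Set, so the infant denominator may also be below 71.

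**The case against.** The strongest objection is that 'reached' does not mean 'attended'. The triggers in the same two sections use 'completed' for visits that must have taken place. 'Reached' can fairly be read as a follow-up cut-off, and subjects who died or withdrew would then stay in once their time had passed. Sections 4 and 5.3 already fix the safety sets, while section 7 deals with timing. This makes the literal exclusion uncertain. It does not settle the matter, because the SAP never states the cut-off reading, ties the condition to a visit, and has no clause keeping early deaths or withdrawals.

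A reader might also infer that an imbalance in early deaths could not be detected at all. The documents do not support that:

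- An unblinded IDMC monitors safety under its own SAP (section 3).
- The final by-group analysis uses all endpoint data (7.1.4).
- All-subject SAE and AESI listings are promised at both analyses. They carry no group, and the same sections then rule out by-subject listings except for SUSARs, so they are only a partial safeguard.
- After a stillbirth the mother can still reach Day 43, so that outcome is not lost on the maternal side.
- Results that would unblind a subject, such as an AE in one subject only, have their group withheld. A single death might therefore go unattributed even on the Exposed Set.

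Nor is the difference from the first analysis a contradiction in itself. That analysis is triggered by Day 31 and delivery, when few subjects would have passed Day 43. The conflict that stands is with 5.3.1.

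**Conclusion.** The point holds as a defect of wording with a possible effect on interim safety tables. As written, 7.1.2 and 7.1.3 allow, and on a literal reading require, selection on survival and retention inside the primary safety window, and they do not agree with 5.3.1. It should be fixed. It is not critical to the trial, because the interim analyses are descriptive (7.2), no stopping or dose rule in these sections depends on them, and the final analysis and IDMC review do not change.

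The contrast of 0/69 with 2/71 rests on four assumptions: the literal reading, 71 per group at the third analysis, two deaths in one group, and no masking of the result. The SAP supplies no rate of death or withdrawal, so the figures show what the rule could hide and do not predict what it did hide.

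**What to change.** In 7.1.2 and 7.1.3, replace the visit condition with one of the following:

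1. The Exposed Set (Solicited Safety Set for solicited events) with all available data, as in 7.1.1. This also restores agreement with 5.3.1.
2. A calendar-time cut-off: all Exposed mothers and infants whose Day 43 post-delivery date plus window has passed at the data cut-off, whether or not the visit took place. Where no delivery date is known, as for a mother who died or withdrew before delivery, use the estimated delivery date, which section 9.1.1 already uses for gestational age.

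Under either option, state that subjects who died, withdrew or were lost before Day 43 remain in numerator and denominator. If the cut-off reading was always intended, option 2 only writes it down.

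The cost is a sentence in each section and one population flag, with no new data. The existing masking rule can stay.
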